	
Statistical analysis, data listings, graphs and summary tables will be produced using SAS®, version 9.2 or above.
 
Full details, including the use of the matched control database(s), of the interim and final statistical analyses to be performed will be described in detail in the Statistical Analysis Plan (SAP).

--	---

DRAFT

Table 1-1: Schedule of Assessments

	Initiation visit Day 0 (Baseline)	Daily data collection	Weekly data collection	Monthly data collection	Follow up visits (every 3 months ^a)
Pre-read of patient information sheet and informed consent document	X				
Written Informed Consent	X				
Check of inclusion/exclusion criteria	X				
Demographic data	X				
Medical history	X				X
Standard of care medication (number of doses given in previous period of time)	X		X		X
Site of pain reported in NRS	X		X		X
Additional efficacy assessments			X		
Quality of life score	X				X
Blood reports ^b	X				X
Genetic test for cannabis tolerance validation study	X				
Continuous cannabis intolerance assessments: red flags		X			X
Overall assessment of efficacy and tolerability			X		X
Scan or additional tests ^b	X				X
Determination of state of disease	X				X
Adverse events	X	X	X		X
Prescription and treatment regimen compliance	X		X		X

a. Follow-up visit can be done in person or over the phone. If available.

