The inhaled route of delivery is the most controllable and predictable route of delivery for the administration of CBMPs. Heating a 250 mg sachet of CBMP in the medical grade vaporisers produces vapor which contains consistent quantities of active phytochemicals, is quickly absorbed with rapid onset of action. The rapid kinetics allow a faster dose titration, enabling the correct dose to be achieved while minimising side effects. Importantly, vaporised CBMP produces blood levels of active ingredients, principally THC and CBD, with a relatively short duration of activity (up to 1 hour), which reduces the risk of a long-lasting side effects, of importance if the subject receives an accidental overdose. This is a distinct advantage over other routes of delivery such as oral and sublingual which have substantially longer durations of activity (6 to 8 hours).

Table 1) List of eight major cannabinoids found in medical cannabis in their active decarboxylated forms

Name (abbreviation)	Structure
(-)-trans- Δ^9 -tetrahydrocannabinol (THC)	
Cannabidiol (CBD)	
CBG	
CBN	
CBC	
THCV	
CBDV	
CBGV	

In cannabis, alongside cannabinoids, there are 11 major terpenes (α -pinene, β -pinene, β -myrcene, limonene, terpinolene, linalool, α -terpineol, β -caryophyllene, α -humulene, and caryophyllene oxide) (Ibrahim et al., 2019). It is thought these compounds in various concentrations interact with cannabinoids to produce the variety of medicinal effects found in the cannabis strains used by medicinal cannabis patients (Russo, 2011), through the entourage effect.

There are strains that produce high levels of THC and low levels of CBD, strains that have the opposite profile and strains that are balanced. The medical cannabis community describe products in terms of their THC and CBD content:

- 1) High THC (>10 %) / low CBD (<3 %)
- 2) Mid THC / mid CBD (balanced THC to CBD, at approximately 10 %)
- 3) Low THC (<3 %) / high CBD (>10 %).

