Trial subjects will come from patients who have consented to receive treatment at the Harley Street (CPC) clinic. The study will consist of an initiation visit (or call) to allow screening and base line data to be taken and then a follow up visit (or call) every three months thereafter, until the end of the study (after the last subject's 3 years of treatment). Day 0 (baseline) for each subject will be the initiation visit when study treatment is started (first prescription written) (see figure 1). Prior to conducting any data collection, eligibility for enrolment will be assessed, oral consent will be requested for conductance of a genetic test and if appropriate a pregnancy test. A full medical history will be taken to assess suitability for treatment with medical cannabis; focusing on pain aetiology, subject's current standard of care and previous history of medical cannabis, if any use. Each participant will be provided with study documents to allow them to consider whether they want to have their data collected prior to providing written informed consent.

Informed consent documents (consent form and patient information sheet) will be sent to patients at least 2 days prior to the initial consultation to allow patients time to review them. At the time of initial consultation, the clinician will review the documents with the participant again and explain them in detail. If the subject agrees to provide informed consent, the clinician will witness the subject signing the consent form. If this takes place over video conference the clinician will witness and record the signing event. In addition, the subject will provide photographic identification prior to consultation, permitting confirmation of the participants identification at the time of the remote consultation. Free prescriptions for the study regimen will be provided. Subjects will provide saliva samples for genetic single nucleotide polymorphism (SNP) genetic analysis to study the genetic risk of an individual's sensitivity to THC. Subjects will be continuously monitored via real time reporting of patient reported outcomes and cannabis use information delivered by vaporiser and its bluetooth connected mobile phone application. Tolerability-related patient reported outcome

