In order to reduce bias and to balance the distribution of covariates in the treated and control groups, multiple regression analysis will be used adjusting for potential confounders. Matching methods such as propensity scoring methods may also be used. The propensity score facilitates the construction of matched sets with similar distributions of the covariates, without requiring close or exact matches on all of the individual variables. However, unmeasured confounding may still be present after matching and should be recognized as a limitation.

Baseline Controls

All analyses will be baseline-compared (i.e. using changes from baseline).

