6.6.1 Assessments during the study

- **Initiation visit/call (Day 0)**

Day 0 (baseline) for each subject will be the initial clinic visit when treatment is started. Alongside the daily monitoring of CBMP tolerability through the patient reported outcomes,

subjects will have 3 monthly consultations..

- Complete medical questionnaire form
- Review of medical history and relevant investigations
- Review current treatment being received or proposed
- Assess inclusion and exclusion criteria
- Written informed consent obtained
- Discuss the medicinal cannabis therapy
- Go through dosing instructions with participants (i.e., how to use the device, when to use the CBMP and how to enter data onto their smart device).
- If appropriate arrange the prescription

Daily assessments (concomitant with dosing)

- Tolerability NRS measurements (anxiety, drowsiness, dizziness, shortness of breath)

The tolerability measures collected 30 minutes after dosing with the CBMP are collected and fed back to Heydoc. Any NRS score >5 causes an alert, which triggers a study physician to contact the subject to assess their status and to elicit an appropriate response.

Weekly assessments

- Efficacy NRS measurements (pain, well-being, sleep quality, fatigue, nausea, depression, appetite)
- Global impression of change

3 monthly assessments

- Quality of life (SF-12)

3 monthly visits/call

- Review of efficacy and tolerability of medicinal cannabis and establishing the subject's overall impression on how they have responded to the CBMP
- Review current treatment being received or proposed
- Adverse events
- Renew prescriptions. Remind the participants of dosing instructions

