6.7 Effectiveness, tolerability and safety measurements

6.7.1 Effectiveness measurements

Change from baseline in pain intensity (pain NRS).

Change from baseline in quality of life measure (SF-12)

Change from baseline in well-being (well-being NRS)

Change from baseline in fatigue (fatigue NRS)

Change from baseline in nausea (nausea NRS)

Change from baseline in depression (depression NRS)
Change from baseline in anxiety (anxiety NRS)
Change from baseline in appetite (appetite NRS)
Change from baseline in sleep quality (sleep NRS)
Change from baseline in use of concomitant pain medications
Patient's global impression of change (PGIC)

Generally, these quarterly reports compare the results to the previous quarterly results and the Specialist can make comments about the changes from the previous period.

Numerical data will be collated and reports made on the baseline changes for pain, QoL, well-being, fatigue, nausea, depression, appetite, sleep quality, anxiety, global impression of change and concomitant medication, to define whether the subject has received benefit.

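### Seven of the ten measures to be analysed as change from baseline have no Day 0 assessment, anxiety and dizziness are scheduled only once treatment has started, and a planned confusion outcome is never collected

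*Protocol*

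**What the plan says.** Section numbers refer to Appendix 1 (the CANPAIN protocol) unless the main feasibility protocol is named.

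- **Rule.** Section 6.2: "All analyses will be baseline-compared (i.e. using changes from baseline".
- **Measures.** Section 6.7.1 lists ten changes from baseline, for example "Change from baseline in sleep quality (sleep NRS", and says the collated changes serve "to define whether the subject has received benefit".
- **Planned analyses.** Section 9.5.1.1 names changes in quality of life, sleep, anxiety, confusion, dizziness and concomitant medicines, with change from baseline at several time points including 12 months.
- **Schedule.** Table 1-1 marks Day 0 for standard of care medication, the pain NRS and quality of life. The row "Additional efficacy assessments" has a weekly mark only. The cannabis intolerance row is marked daily and at 3-monthly follow-up.
- **Assessments in prose.** Section 6.6.1 gives the weekly set as "Efficacy NRS measurements (pain, well-being, sleep quality, fatigue, nausea, depression, appetite". Anxiety and dizziness are in the daily set: "The tolerability measures collected 30 minutes after dosing with the CBMP". Its Day 0 list names none of these scales.
- **Baseline date.** Section 6.1: "Day 0 (baseline) for each subject will be the initiation visit when study treatment is started (first prescription written". Figure 1, Stage 4, however, has patients invited during the clinic treatment phase and following the study protocol only after they join.
- **Clinic pathway.** The main protocol, section 2, requires questionnaires before first use for pain and quality of life only.

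**The concern.** A change from baseline needs a value recorded before treatment can act. For most of these measures the schedule does not require one.

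For the six weekly scales, the first score may fall before or after the first dose. If after, any early effect becomes part of the reference value. For anxiety and dizziness the problem is sharper: section 4.1 describes the vaporised product as acting "with a relatively short duration of activity (up to 1 hour", so a 30-minute score sits inside the period of drug effect. Used as baseline, it would hide the acute effects that the tolerability objective is meant to detect. Section 4.2.1 also plans to relate reported anxiety to genetic markers of THC sensitivity. Without a pre-dose score, existing anxiety cannot be separated from induced anxiety.

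Patients who join after starting treatment bring, at most, the pre-use pain and quality-of-life questionnaires from the clinic pathway. Nothing stated supplies the other scales for them.

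**Working it through.** No stated figure has to be reproduced. The check maps each planned change outcome to its Table 1-1 row and compares that with 6.6.1.

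| Outcome | Listed in | Table 1-1 marks | Day 0? |
|---|---|---|---|
| Pain NRS | 6.7.1 | Day 0, weekly, 3-monthly | Yes |
| Quality of life (SF-12) | 6.7.1, 9.5.1.1 | Day 0, 3-monthly | Yes |
| Concomitant pain medication | 6.7.1, 9.5.1.1 | Day 0, weekly, 3-monthly | Yes |
| Well-being | 6.7.1 | Weekly | No |
| Fatigue | 6.7.1 | Weekly | No |
| Nausea | 6.7.1 | Weekly | No |
| Depression | 6.7.1 | Weekly | No |
| Appetite | 6.7.1 | Weekly | No |
| Sleep quality | 6.7.1, 9.5.1.1 | Weekly | No |
| Anxiety | 6.7.1, 9.5.1.1 | Daily, 3-monthly | No |
| Dizziness | 9.5.1.1 | Daily, 3-monthly | No |
| Confusion | 9.5.1.1 | No row | Never collected |

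Global impression of change is left out because it is not a change from baseline.

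**Counts**

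- 6.7.1: 10 measures, 3 with a Day 0 mark; 10 − 3 = 7 without (6 weekly + anxiety); 7/10 = 70%.
- 9.5.1.1: 6 named changes; 2 with a mark (quality of life, concomitant medicines), 3 without (sleep, anxiety, dizziness), 1 not collected (confusion).
- Both lists: 10 + dizziness + confusion = 12; 3 with a mark; 6 weekly + 2 in the daily set + 1 not collected = 9 without; 9/12 = 75%.

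**Does the mapping matter?** The protocol does not define the row that is read here as the six weekly scales. If that row meant something else, those scales would have no row at all and still no Day 0 mark. If anxiety belonged with the weekly scales, it would again have no Day 0 mark. The count stays at 7 of 10.

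**Is the empty cell an extraction fault?** No. The row's column positions are intact, and 6.6.1 independently places these scales in weekly or daily collection.

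**Effect on the estimate.** Let *b* be a patient's true pre-dose score, *e*₁ the treatment effect present at the first recorded score, and *e*ₜ the effect at time *t*.

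- With a pre-dose baseline: change = (*b* + *e*ₜ) − *b* = *e*ₜ.
- With the first on-treatment score as baseline: change = (*b* + *e*ₜ) − (*b* + *e*₁) = *e*ₜ − *e*₁.

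The error is −*e*₁. For a 30-minute anxiety score with a constant acute effect, *e*ₜ = *e*₁ and the computed change is zero whatever that effect is. The documents give no value for *e*₁, so the error cannot be put in NRS points.

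**The case against.** Several points can fairly be made for the plan.

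- **General baseline provisions.** Section 6.1 provides for baseline data at the initiation visit and for some retrospective collection, and the Day 0 list includes a medical questionnaire form. None of these names the scales in question, and Table 1-1 leaves their Day 0 cells empty.
- **Figure 1.** Only Stage 4 is legible in the available text, so an earlier stage might show more. That limits the claim to what the readable text requires. It does not alter Table 1-1 or 6.6.1.
- **Delivery delay.** The product is couriered after prescription, so a first weekly entry could precede first use. Nothing requires this or designates that entry as baseline.
- **Anxiety.** The synopsis lists it both as an effectiveness variable and as a daily THC effect, so its absence from the weekly list may be an oversight. The 3-monthly tolerability mark is not tied to the 30-minute window. Neither supplies a pre-dose value. The safety alert works on an absolute score above 5 and is unaffected.
- **Confusion.** This may be a slip: drowsiness is collected but not named in 9.5.1.1. It still needs correcting.
- **Weight.** The outcomes are secondary and descriptive, in a text marked as a draft for a future submission. This stands and limits the importance of the point.

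Leaving the definition of baseline to the SAP would not help: it can choose among collected values, but it cannot create one.

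**Conclusion.** The concern holds. Followed as written, the schedule guarantees no pre-treatment value for 7 of the 10 measures in 6.7.1, or for 9 of the 12 change outcomes when 9.5.1.1 is included. One of those 12 has no measurement at all. The count assumes that Table 1-1 and 6.6.1 are the complete schedule; no readable part of the document contradicts that.

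The size of any bias cannot be derived, and understatement of acute anxiety or dizziness follows only if an on-treatment score is used as baseline. The primary pain NRS has a Day 0 assessment, and the feasibility objectives do not use these change scores. This is therefore a mismatch between schedule and analysis to correct before CANPAIN starts; it does not threaten the primary comparison. It deserves attention now because the missing values could not be recovered later.

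**What to change.** 1. In Table 1-1 and 6.6.1, add a baseline score for well-being, fatigue, nausea, depression, appetite, sleep quality, anxiety and dizziness, completed before the first dose in the same session as the existing pain and SF-12 questionnaires.
2. Reconcile 6.1 with Figure 1, Stage 4, and state whether pre-dose scores collected by the clinic serve as study baseline for patients who join after starting treatment.
3. State whether the effectiveness analysis of anxiety uses a score not timed to dosing; otherwise remove anxiety from 6.7.1.
4. In 9.5.1.1, either define and schedule a confusion score or delete it.

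For treated patients the cost is a table edit, a sentence on baseline timing and eight one-line app questions asked once, with no added visit. Section 6.2 says control data mirror the CANPAIN data apart from tolerability, so the added effectiveness items would also be needed once at entry for controls. That is a small extra burden per person, but it extends to the control sites.

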3. LIST OF ABBREVIATIONS AND DEFINITION OF TERMS

3.1 List of Abbreviations

2-AG	2-arachidonoylglycerol
ADT	Abstract Data Type
AE	Adverse Event
AERS	Adverse Effects Reporting System
aHR	adjusted Hazard Ratio
CA	Competent Authority
CB1	Cannabinoid receptor type 1
CB1A	Cannabinoid receptor type 1A
CB2	Cannabinoid receptor type 2
CB2A	Cannabinoid receptor type 2A
CBC	Cannabichromene
CBD	Cannabidiol
CBDV	Cannabidivarin
CBG	Cannabigerol
CBGV	Cannabigerivarin
CBMP	Cannabis based medicinal product
CBN	Cannabinol
CCI	Chronic Constriction Injury
CD4	Cluster of differentiation 4
CD8	Cluster of differentiation 8
CFA	Complete Freund's Adjuvant
CI	Confidence interval
CINV	Chemotherapy Induced Nausea and Vomiting
CNS	Central Nervous System
COMT	Catechol-O-Methyltransferase
CPC	Care Pain Clinic
CRF	Case Report Form
CUD	Cannabis use disorder
CXCR4	C-X-C chemokine receptor type 4
CYP1A2	Cytochrome P450 1A2
CYP3A4	Cytochrome P450 3A4
CYP2B6	Cytochrome P450 2B6
CYP2C9	Cytochrome P450 2C9
CYP2C19	Cytochrome P450 2C19
ECS	Endocannabinoid system

ePRO	electronic Patient Reported Outcome
ERK1/2	Extracellular signal-regulated kinases 1/
GCP	Good Clinical Practice
GMC	General Medical Council
GPCR	G protein coupled receptor
HHV	Healthy Human Volunteer
HIV	Human Immunodeficiency Virus
IBD	Inflammatory Bowel Disease
IGSoC	Information Governance Statement of Compliance
IL-1 β	Interleukin-1beta
IL-6	Interleukin-6
ITT	Intention to Treat
LAR	Legally Authorized Representative
MAPK	Mitogen-activated protein kinase
MDI	Meter Doses Inhalers
MEDD	Morphine equivalent daily dose
MedDRA	Medical Dictionary for Regulatory Activities
MHRA	Medicines and Health Products Regulatory Agency
mmHg	millimetres of mercury
NK	Natural Killer
NRS	Numerical Rating Scale
ODD	Opioid Use Disorder
PEA	Palmitoylethanolamide
PGIC	Patient's Global Impression of Change
PNL	Partial Sciatic Nerve Ligation
PP	Per Protocol
PPAR	Peroxisome Proliferator Activating Receptor
PPAR γ	Peroxisome Proliferator Activating Receptor Gamma
PRN	Pro Re Nata
PT	Preferred Term
QoL	Quality of Life
RCT	Randomised Controlled Trial
REC	Research Ethics Committee
SAEs	Serious Adverse Effects
SAF	Safety Analysis Set
SAP	Statistical Analysis Plan
SAS	Statistical Analysis System (Software)

SD	Standard Deviation
SF-12	12 item short form health survey
SNL	Spinal Nerve Ligation
SOC	System Organ Class
SOP	Standard Operating Procedure
SSL	Secure Socket Layer
SUSARs	Suspected Unrelated Serious Adverse Reactions
THC	Δ 9-tetrahydrocannabinol
THC-acid	2-COOH- Δ 9-tetrahydrocannabinol
THCV	Tetrahydrocannabivarin
TNF α	Tumour Necrosis Factor alpha
TRPM8	Transient receptor potential cation channel subfamily M member 8
TRPV1	Transient receptor potential cation channel subfamily V member 1
UV	Ultraviolet
WMA	World Medical Association

3.1 Definitions of terms

Treatment regimen:	All participants will be given the same regimen for each chronic pain disease outlined in this protocol.
Abstinence:	Refraining from heterosexual intercourse during the entire period of risk associated with the study treatments
Acceptable contraception methods:	
Birth control methods which may be considered as highly effective, achieving a failure rate of less than 1% per year when used consistently and correctly, include:
 
Combined (estrogen and progestogen containing) hormonal contraception associated with inhibition of ovulation¹ (oral, intravaginal, transdermal). Progestogen-only hormonal contraception associated with inhibition of ovulation (oral, injectable, implantable²). Intrauterine device (IUD)². Intrauterine hormone-releasing system (IUS)². Bilateral tubal occlusion². Vasectomised partner^{2,3}. Sexual abstinence⁴.
 
Acceptable contraception method but may not be as highly effective, that result in a failure rate of more than 1% per year include:
 
Progestogen-only oral hormonal contraception, where inhibition of ovulation is not the primary mode of action. Male or female condom with or without spermicide⁵. Cap, diaphragm, or sponge with spermicide⁵.
 
¹ Hormonal contraception may be susceptible to interaction with the IMP, which may reduce the efficacy of the contraception method. ² Contraception methods that in the context of this guidance are considered to have low user dependency. ³ Vasectomised partner is a highly effective birth control method provided that partner is the sole sexual partner of the trial participant and that the vasectomised partner has received medical assessment of the surgical success. ⁴ In the context of this guidance sexual abstinence is considered a highly effective method only if defined as refraining from heterosexual intercourse during the entire period of risk associated with the study treatments. The reliability of sexual abstinence needs to be evaluated in relation to the duration of the clinical trial and the preferred and usual lifestyle of the subject. ⁵ A combination of male condom with either cap, diaphragm or sponge with spermicide (double barrier methods) are also considered acceptable but not highly effective, birth control methods

Unacceptable contraception methods:	Periodic abstinence (calendar, symptothermal, post-ovulation methods), withdrawal (coitus interruptus), spermicides only, and lactational amenorrhoea method (LAM) are not acceptable methods of contraception. Female condom and male condom should not be used together.
Women of child bearing potential:	For the purpose of this document, a woman is considered of childbearing potential (WOCBP), i.e. fertile, following menarche and until becoming postmenopausal unless permanently sterile. Permanent sterilisation methods include hysterectomy, bilateral salpingectomy and bilateral oophorectomy. A postmenopausal state is defined as no menses for 12 months without an alternative medical cause. A high follicle stimulating hormone (FSH) level in the postmenopausal range may be used to confirm a post-menopausal state in women not using hormonal contraception or hormonal replacement therapy. However, in the absence of 12 months of amenorrhoea, a single FSH measurement is insufficient.
End of the trial:	The length of the trial for each participant is a maximum of 3 years.

4. INTRODUCTION

4.1 Background of the trial

On the 1st of November 2018 the Home Office in response to guidance from the Chief Medical Officer and the Department of Health, announced that cannabis-based products for medicinal use were to be moved from Schedule 1 to Schedule 2 status in the misuse of drugs regulations, reflecting the view that these agents possess medical utility.

Due to its unlicensed status, medical cannabis must be prescribed in clinical practice through a 'Specials License' and prescribing must remain wholly under the control of a GMC registered Specialist, who have been made responsible for determining who is eligible to receive medical cannabis, satisfying two predetermined criteria: 1) that unmet clinical need exists and that there must be enough evidence that the subject would receive benefit, and 2) the subject must have exhausted all other established treatment options. Specialists should possess the correct knowledge to determine whether all established treatment options have been exhausted or inappropriate. However, in addition to this, most specialists will need training on the evidence base and the current clinical approach to the use of medicinal cannabis.

Cannabis derives from two main strains of plant; *Cannabis Sativa* and *Cannabis Indica*. Over the last 50 years, these strains have been repeatedly cross bred to create many new varieties and hybrids each with unique chemical compositions. Chemically, cannabis strains are immensely complex, with cannabinoids and other phytochemicals, making up a large array of biologically active compounds all with potential clinical utility. Most of the cannabis research has focused on cannabinoids, of which almost 200 have so far been identified (Hanus et al., 2016). Eight of these cannabinoids are thought to be responsible for most of the effects of medicinal cannabis and so are routinely measured (Aizpurua-Olaizola et al., 2016). There is now acceptance that cannabis has demonstrable medical utility, at varying levels of evidence quality, in conditions including chronic pain, multiple sclerosis, anxiety, depression, sleep disorders, inflammatory bowel disease (IBD) and epilepsy (Barnes and Barnes, 2016). However, due to the plant's chemical complexity it is difficult to fully define which chemicals contribute to the pharmacology of cannabis. Much scientific work is underway to elucidate this.

Cannabinoids are synthesised by the plant in a carboxylic acid form, for example THC exists as THC-acid. To exert a pharmacological effect, carboxylic acids require conversion to their decarboxylated forms through either heat or light (Wang et al., 2016). The literature indicates that THC and CBD are of primary importance in eliciting the clinical effects of medical cannabis. There is substantial peer-reviewed evidence which supports the utility of medical cannabis. The evidence for some of its individual constituents (primarily THC and CBD) for treating diseases and their symptoms, will be outlined in detail.

Cannabis flower, hashish and whole plant extracts currently predominate in medical cannabis therapy, although the production of isolated cannabinoids is currently being investigated through chemical and biotechnology routes of synthesis. Current products are derived from strains of cannabis which produce, in the flower, high concentrations of the eight major cannabinoids in varying ratios and amounts (see table 1). The two cannabinoids that are predominantly focused on, due to their relative abundance and complimentary pharmacological profiles are THC and CBD.

It is essential that CBMPs are safe and reliable pharmaceutical grade products and must be produced to good manufacturing practice (GMP) standard. To satisfy these requirements, CBMPs are tested to confirm that they are derived from a cannabis plant and that it contains the principle

active ingredients, listed in the product's predefined specification. CBMPs may require gamma irradiation to sterilize them and are tested for the presence of microorganisms harmful to health. Additionally, CBMPs are tested for the presence of pesticides, heavy metals and must be free of these harmful substances as well as contaminants such as soil. The total water content must be below a predefined specification to ensure it is suitable for vaporisation.

The inhaled route of delivery is the most controllable and predictable route of delivery for the administration of CBMPs. Heating a 250 mg sachet of CBMP in the medical grade vaporisers produces vapor which contains consistent quantities of active phytochemicals, is quickly absorbed with rapid onset of action. The rapid kinetics allow a faster dose titration, enabling the correct dose to be achieved while minimising side effects. Importantly, vaporised CBMP produces blood levels of active ingredients, principally THC and CBD, with a relatively short duration of activity (up to 1 hour), which reduces the risk of a long-lasting side effects, of importance if the subject receives an accidental overdose. This is a distinct advantage over other routes of delivery such as oral and sublingual which have substantially longer durations of activity (6 to 8 hours).

Table 1) List of eight major cannabinoids found in medical cannabis in their active decarboxylated forms

Name (abbreviation)	Structure
(-)-trans- Δ^9 -tetrahydrocannabinol (THC)	
Cannabidiol (CBD)	
CBG	
CBN	
CBC	
THCV	
CBDV	
CBGV	

In cannabis, alongside cannabinoids, there are 11 major terpenes (α -pinene, β -pinene, β -myrcene, limonene, terpinolene, linalool, α -terpineol, β -caryophyllene, α -humulene, and caryophyllene oxide) (Ibrahim et al., 2019). It is thought these compounds in various concentrations interact with cannabinoids to produce the variety of medicinal effects found in the cannabis strains used by medicinal cannabis patients (Russo, 2011), through the entourage effect.

There are strains that produce high levels of THC and low levels of CBD, strains that have the opposite profile and strains that are balanced. The medical cannabis community describe products in terms of their THC and CBD content:

- 1) High THC (>10 %) / low CBD (<3 %)
- 2) Mid THC / mid CBD (balanced THC to CBD, at approximately 10 %)
- 3) Low THC (<3 %) / high CBD (>10 %).

The safety profile of cannabis has been extensively studied revealing that the majority of adverse events are attributable to one of its constituents, THC. THC induces acute adverse effects such as anxiety and chronic effects such as increased risk of psychosis and addiction/dependence (D'Souza et al., 2004; Zehra et al., 2018). The acute effects are largely avoidable if either the dose is kept low (<3 mg per day) or the cannabis extract has enough CBD to counteract THC-induced anxiety (MacCallum and Russo, 2018). The risk of long-term psychoses and depression is substantially reduced if the cannabis is not used during adolescence (Gobbi et al., 2019). The addiction potential of cannabis has also been well studied and in susceptible individuals, chronic dosing of very high THC strains of cannabis can lead to addictive behaviour (termed cannabis misuse disorder). To minimise risk, it is essential to; 1) restrict access by the paediatric patient population, 2) ensure that starting doses are kept low, particularly for THC high products, 3) use balanced THC: CBD cannabis products and 4) monitor the quantity of medicinal cannabis consumed to ensure excessive consumption is limited.

These strategies are designed to limit the risk of addictive behaviour and psychoses in susceptible individuals. Whilst there is evidence that THC has health benefits, certain individuals have increased risk of acute anxiety and dependence with chronic use. There is emerging pharmacogenetic evidence for determinants of susceptibility for THC-induced anxiety. Polymorphisms in effector, metabolism and ancillary genes effect how individuals respond to THC exposure. CB1 receptor genes are the most widely studied, but other genes controlling metabolism such as CYP3A4 and COMT are also implicated (Hyrhorowicz et al., 2018). As well as complementing the benefits of THC, CBD counteracts THC induced adverse events such as anxiety in susceptible individuals (Russo, 2011). Patients using THC, require a THC/CBD ratio that provides the right pharmacological effect, while minimising that individual's risk of THC induced psychological morbidity.

CBD when given without THC, need to be given in high doses to achieve a therapeutic effect (300 mg to 1000 mg per day), and when used on its own it is associated with adverse events such as somnolence, GI upset and the more serious but rarer adverse event of raised liver enzymes (Stockings et al., 2018).

Whilst it is very important to address the addiction potential of medicinal cannabis, it is also important to emphasise that the risks associated with cannabis are comparatively lower than other analgesics utilised in chronic pain conditions, namely opioids and other anti-neuropathic agents. Medicinal cannabis is now considered to be a potential adjunct to opioid based analgesia, boosting opioid efficacy and there is evidence that the addition of medicinal cannabis lowers the dose and time required to reach analgesia for opioids, reducing dose burden and moving patients away from opioid use disorder (OUD) (Wiese and Wilson-Poe, 2018).

The pharmacokinetics of CBD and THC have been thoroughly described (Sativex product monograph). THC and CBD are both absorbed and metabolized in a similar manner. They have poor oral bioavailability (around 6%), are both widely distributed into lipid tissues due to their highly lipophilic physicochemical properties and also demonstrate high protein binding (~97%). They are both primarily metabolised by cytochrome P450 enzymes (CYP3A4, 1A2, 2B6, 2C9 and 2C19), with relatively short initial half-life of about 5 hours but a long terminal half-life of between

24 and 36 hours. The primary differences that exist for medicinal cannabis products are the route of delivery. Inhaled cannabis is rapidly absorbed (T_{max} = ~10 minutes) and has a relatively rapid initial half-life (1 to 2 hours), while cannabis ingested through the oral route has a much-delayed absorption kinetic (T_{max} = 1 to 2 hours) and importantly higher levels of the high potency psychoactive metabolite 11-OH-THC are present after oral absorption (Sharma et al., 2012), which increases the risk of this route of delivery for THC sensitive individuals.

The aim of our clinical study is to provide cannabis based medical product in the form of cannabis flower with mid-levels of THC (8%) balanced by 8% CBD given to subjects with an unmet clinical need through a single route of delivery (vaporised; inhaled) under the medical guidance for a GMC registered specialist clinician. We will collect data from subjects receiving medicinal cannabis therapy; assessing how participants respond, how well they tolerate it and their patterns of use. Data will be collected via connected devices and validated ePRO tools. In addition, data regarding side effects will be collected and reported in a timely manner.

